2.2.4 Baseline imaging and circulating ATL cell count

- CT scan of the neck, chest, abdomen and pelvis
- Other imaging studies may be done to document disease as appropriate and at the direction of the PI.
- Determination of marker lesion measurements as per ATL International Consensus meeting³.

2.2.5 FACS analysis for circulating CD3^{dim} CD4⁺ cells (see Section [3.4.1.6](#))

2.2.6 Documentation of Karnofsky or ECOG Performance Score ([APPENDIX A](#)).

2.2.7 Pathology confirmed by the Laboratory of Pathology, NCI prior to registration.

- Pathological confirmation of diagnosis can be carried out on available slides from either the primary diagnostic biopsy or subsequent biopsies performed at the Clinical Center or outside institutions.
- For the subset of patients who do not have circulating abnormal cells a lymph node or skin biopsy will be obtained for diagnostic purposes and to evaluate the expression of the CD25 (Tac) on the malignant cells.
- Patients with suspected skin involvement from ATL should have skin biopsies. All skin or lymph node biopsies should be submitted fresh in saline to the Hematopathology Section of the Laboratory of Pathology.
- Biopsy specimens will be processed for routine histopathology as well as immunohistochemistry in frozen sections and/or flow cytometry for expression of CD25 (Tac) and other lymphocyte surface antigens.
- Lymph node aspirates will be handled as per the standard procedures of the cytology section.
- If the original pathological material or other diagnostic biopsies are not available, or if there is uncertainty concerning the diagnosis, a repeat biopsy may be undertaken to confirm the diagnosis of ATL.

- 2.2.8 Complete blood count (CBC) with differential, platelet count and reticulocyte count.
- 2.2.9 Acute Care panel (sodium, potassium, chloride, CO₂, glucose, BUN, creatinine).
- 2.2.10 Hepatic panel (alkaline phosphatase, ALT, AST, total and direct bilirubin), LDH, and mineral panel (serum calcium, phosphate, magnesium and albumin).
- 2.2.11 Serum pregnancy test in women of childbearing potential.
- 2.2.12 Hepatitis B Surface Antigen, Hepatitis B Surface Antibody, Hepatitis B core Antibody, Hepatitis B DNA Quantitative, and Hepatitis C: HIV 1/2 and HTLV-I/II serology.

2.3 PARTICIPANT REGISTRATION AND STATUS UPDATE PROCEDURES

Registration and status updates (e.g., when a participant is taken off protocol therapy and when a participant is taken off-study) will take place per CCR SOP ADCR-2, CCR Participant Registration & Status Updates found [here](#).

NOTE: Patients previously treated with the standard 20-mg twice daily dose who came off protocol for disease progression are eligible to re-enroll and be treated at the higher doses. These re-enrolled patients will be given new patient numbers to clarify their treatment outcomes for each of the 2 treatment regimens (standard vs. dose escalated).

2.3.1 Treatment Assignment and Randomization/Stratification Procedures

2.3.1.1 Cohorts

Number	Name	Description
1	T-Cell Leukemia patients (CLOSED)	HTLV-associated smoldering, chronic, or clinically indolent T-cell leukemia (ATL) (12 subjects)
2	T-Cell Leukemia patients – Dose Escalation	HTLV-associated smoldering, chronic, or clinically indolent T-cell leukemia (ATL) (up to 20 subjects)
3	T-Cell Leukemia patients – Dose Expansion	HTLV-associated smoldering, chronic, or clinically indolent T-cell leukemia (ATL) (up to 6 subjects)

2.3.1.2 Arms

Number	Name	Description
1	Experimental Treatment (CLOSED)	Ruxolitinib 20mg orally twice daily for 28 days. Patient may continue to receive treatment until PD.
2	Experimental Treatment – Dose Escalation	Ruxolitinib 30-50 mg orally twice daily for 28 days to determine the maximum tolerated dose (MTD). Patients may continue to receive treatment until PD or unacceptable toxicity.
3	Experimental Treatment – Dose Expansion	Ruxolitinib at the MTD orally twice daily for 28 days. Patients may continue to receive treatment until PD or unacceptable toxicity.

2.3.1.3 Randomization and Arm Assignment

Single arm/group: open-label and non-randomized. New patients in Cohort 2 or 3 directly assigned to treatment arm 2 or 3 based on the arm open at the time of enrollment. **NOTE:** Previously enrolled subjects are allowed to re-enroll on this study.

2.3.2 Screen Failures

Screen failures are defined as participants who consent to participate in the clinical trial but are not subsequently assigned to the study intervention or entered in the study. A minimal set of screen failure information is required to ensure transparent reporting of screen failure participants, to meet the Consolidated Standards of Reporting Trials (CONSORT) publishing requirements and to respond to queries from regulatory authorities. Minimal information includes demography, screen failure details, eligibility criteria, and any serious adverse event (SAE).

Individuals who do not meet the criteria for participation in this trial (screen failure) because of an eligibility criterion (e.g., laboratory parameter) may be rescreened at the discretion of the investigator.

2.4 BASELINE EVALUATION

The following tests will be done after the patient is enrolled or re-enrolled in the study and within 28 days (except as indicated below) of initiating treatment with ruxolitinib. Tests do not need to be repeated if completed during screening and meet the timeframe for baseline evaluation.

- 2.4.1 Complete blood count (CBC) with differential, platelet count and reticulocyte count (within 2 weeks).
- 2.4.2 Acute Care Panel (sodium, potassium, chloride, CO₂, glucose, BUN, creatinine) and C-Reactive Protein (within 2 weeks).
- 2.4.3 Hepatic panel (alkaline phosphatase, ALT, AST, total and direct bilirubin), LDH, and mineral panel (serum calcium, phosphate, magnesium and albumin) (within 2 weeks).
- 2.4.4 Pretreatment assessment of circulating ATL cells present in the PBMC by Cellavision differential (see Sections [3.4.1.4](#) and [3.4.1.6](#), and [Table 4](#)) for T-cell receptor gamma (TCR γ) gene rearrangement to detect clonality (see Section [5.1](#)).
- 2.4.5 CMV serology and CMV antigens
- 2.4.6 FACS, Inflammatory marker and cytokine analysis
 - Baseline flow cytometry to assess lymphocyte sets and subsets (one 10-mL purple-top tubes; see Section [3.4.1.6](#) and [Table 4](#)) to be sent to Flow Cytometry/ Immunology

Laboratory Department of Laboratory Medicine for the Clinical Center. **NOTE:** In case of scheduling conflicts, TBNK may be substituted.

- 2.4.7 In vitro analysis of sensitivity to JAK inhibitors and other molecular therapeutics in 6-day proliferation assay (see Section [5.1.2](#))
- 2.4.8 Serum pregnancy test in women of childbearing potential within 3 days prior to starting the study drug.
- 2.4.9 **Optional Tumor Biopsy:** Patients with easily accessible tumor deposits who consent to this procedure will have a fine-needle aspiration or punch biopsy of one of their tumors for research (see Section [5.1.6](#)). These biopsies may be done by CT guidance.
- 2.4.10 Electrocardiogram
- 2.4.11 Bone marrow aspirate and biopsy will be obtained before treatment (biopsies performed at the Clinical Center within a year prior to treatment may be accepted at the discretion of the Principal Investigator).

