3.5 STUDY CALENDAR

Procedure/ Assessment	Screening	Baseline	Treatment ¹								End of Treatment and Off Study ^{2,17}	
			Cycle 1				Cycle 2		Cycles 3 and 4, and beyond			
			D1	D4-5, D8	D15	D22	D29	D1	D29	D1		
Windows:	D -28 to -1	D -14 to -1			±2 days		±5 days		±10 days			
Ruxolitinib treatment ³					X (daily)							
Informed consent			X									
NCI pathology review/confirmation ⁴	X											
Complete medical history	X											
Physical exam/interval history, Vital signs, Performance status ⁵	X		X	X	X	X		X		X		X
Serum pregnancy test ⁷	X	X	X					X		X		
CBC w/differential	X	X	X	X	X	X		X		X		X
Chemistries panels, LDH and CRP ⁶	X	X	X	X	X	X		X		X		X
Reticulocyte count	X	X										
EKG	X											
Radiographic disease assessment ⁸	X						X		X		X	(X)
Photography for skin lesions (if applicable)	X		X				X		X		X	X
CellaVision differential & FACS assessment: TBNK or lymphocyte subset analysis ⁹	X		X				X		X		X	X
HIV, HTLV, Hepatitis C serology ¹⁰	X											
Hepatitis B serology, Hepatitis B Quantitative DNA ¹⁰	X											X (see footnote)
Bone marrow biopsy and aspirate ¹¹		X										
CMV serology and CMV antigens		X										
Soluble IL-2 receptor alpha, IL-15/IL-15 receptor alpha, IL-18, TNF α ¹²		X	X		X		X		X		X	X
In vitro/PBMC proliferation assays ¹³		(X)	(X)		(X)		(X)		(X)		(X)	(X)
STAT5, phosphoSTAT5 and ruxolitinib levels ¹⁴		(X)	(X)	(X)	(X)		(X)		(X)		(X)	(X)
Molecular analysis of TCR γ chain ¹⁵		X					X				X	X
Optional tumor biopsy ¹⁶		(X)			(X)						(X)	

(X) = Optional

NOTE: Perform additional assessments as clinically indicated. Baseline studies do not need to be repeated if completed during screening and meet the timeframe for baseline evaluation requirements.

1. Each cycle will be 28 days in length. The start of subsequent cycles may be delayed up to 7 days for social occasions or patient's convenience. The patients will be seen in the outpatient clinic twice during the first week (day 1 and day 4 or 5) after starting treatment and

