8. Radiographic restaging for response for patients with radiographically measurable or evaluable disease: CT scan neck, chest, abdomen and pelvis (or other imaging studies as appropriate) on pretreatment for all patients and then day 29 of cycles 1 and 2, and then every 2 cycles for patients who have radiographically measurable or evaluable disease.
9. Cellavision differential and FACS panel shown in **Table 4**, and Sections 3.4.1.6 and 3.4.1.4 for additional details. One 10 mL lavender top tube will be drawn for the FACS panel and sent to the Immunology Lab of the NIH Clinical Center 10/2C410. TBNK can be substituted for scheduling conflicts.
10. HIV and Hepatitis C testing only during screening. Hepatitis B testing as indicated also at screening; patients who have an indolent chronic Hepatitis B infection will have repeat serial Hepatitis B Quantitative DNA and serology every 2 cycles during treatment; this testing may be extended to every 3rd or 4th cycle at the discretion of the investigator after year 1 if the timing for other assessments is adjusted.
11. Patients who are complete responders by FACS evaluation of circulating ATL cells and/or radiographic assessment may have a second BM biopsy (optional) to confirm their response.
12. Samples to assess for IL-2R α IL-18 and TNF α will be drawn in 5mL SST tubes at pre-treatment, on day 15 (if feasible), pre-cycle 2 and 3, at the same time as disease restaging occurs, and at the end of treatment off study visits for all patients. Samples will be held at room temperature until picked up by a Lymphoid Malignancies Branch clinical researcher who will ship the samples to a Contractor for performance of the assays. Serum samples will also be routed by the Department of Laboratory Medicine to Mayo Laboratories for CLIA-certified analysis of soluble IL-2R α levels. See Section 5.1.3 for additional details.
13. In vitro (PBMC) proliferation assays will be an optional test for all patients to potentially be performed pre- and post-treatment on cycle 1 day 1, 15 and 29 and at the time of any subsequent follow-up visit at the PI’s discretion. Up to 50 mL of whole blood will be drawn in a heparinized (green top) tubes. **NOTE:** These assays will not be performed if the absolute lymphocyte count indicates an insufficient number of cells to form these assays at these time points.

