5.1.2 In Vitro Proliferative Assays

NOTE: These samples are optional and will be collected at the discretion of the PI. When collected, the following applies:

Samples for in vitro proliferative assays (PBMCs) will be drawn in a heparinized (green top) tubes (50 mL). The assays will not be performed if the absolute lymphocyte count indicates an insufficient number of cells to perform these assays at these time points. **If there is an insufficient number of circulating cells at these time points, the medical record will indicate this assessment was not performed due to insufficient material and will not be considered a protocol deviation.** Lymphoid Malignancies Branch Clinical Research personnel will pick up these tubes from phlebotomy.

These concentrations of the JAK inhibitors is based on the human pharmacokinetic data to represent a low but achievable *in vivo* drug level and a higher inhibitory level that cannot safely be achieved in patients to assess the drugs' potential inhibitory properties. The effect on proliferation will be assessed by addition of 3 H-thymidine 6 hours before the end of the 6-day cultures. Culture supernatants will be assessed by specific ELISAs for IL-2, IL-9, IL- 15 and IL-21.

These specimens may also be used to perform additional exploratory molecular analyses limited to immune response genes or genes known to be critical to the pathophysiology of HTLV-1 related ATL including but not limited to JAK1, JAK2, JAK3, IRF4, CCR4, NOTCH1 and p53.

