Updated Study Design (Amendment D): Although there were 4 responding patients in the first 12 patient who were treated, the activity was not sustained even in these patients; therefore, we are now changing the treatment regimen to evaluate the activity of augmented dosing (effective with Amendment D). We plan to treat a total of 9 patients at the MTD or MAD and will not proceed with the same original two-stage phase 2 dosing. Patients who discontinue treatment within the first 28 days for reasons other than toxicity will be considered inevaluable. In order to allow for this assessment of patients attempting higher treatment doses, the protocol will require an additional 15-21 patients. Accounting for the previously enrolled 12 subjects, the new design, and to assess up to 9 patients for response at the MTD/MAD level with the new increased dose levels as well as allowing for up to two (2) inevaluable patients: the new accrual ceiling will be set at 35 patients.

The major objective of this study continues to be to determine the antitumor activity of ruxolitinib with regard to response rate and time to progression. Response rate will be based on the number of patients who achieve either a complete or partial response to therapy. Time to progression will be measured from the date of registration until documentation of disease progression..

An exploratory analysis will be performed in the two subgroups of patients defined by the inhibition of their pretreatment *in vitro* ATL cells proliferation by ruxolitinib treatment. The patients will be distinguished on the basis of the results of a 6-day *ex vivo* culture analyses performed on patient peripheral blood mononuclear cells prior to drug administration. One subgroup of patients will be defined as those who fulfill the following criteria: peripheral blood mononuclear cells proliferate *ex vivo* ($\geq 5,000$ CPM/1 μ C) in 6-day culture and their thymidine uptake must be reduced by 40% by the addition of 10 μ M ruxolitinib. The other group of patients would be all the remaining treated patients that do not fulfill these criteria. Since a limited number of patient samples have been assessed to date, it is not clear what percentage of smoldering or chronic stage ATL patients will fulfill the criteria for group 1.

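### The pre-dose proliferation assay that defines the Section 8 subgroups is listed as a baseline test to be done but is optional elsewhere, and untested patients fall into the non-sensitive group by default

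*Combined protocol and SAP*

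**What the plan says.** Section 2.4 opens its baseline list with "The following tests will be done after the patient is enrolled or re-enrolled in the study and within 28 days" of starting ruxolitinib, apart from stated exceptions in timing. Item 2.4.7 is "In vitro analysis of sensitivity to JAK inhibitors and other molecular therapeutics in 6-day proliferation assay". It carries no optional label and refers the reader to Section 5.1.2. The list does mark optional items: 2.4.9 is headed "Optional Tumor Biopsy".

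Three other places give the assay a different status.

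- In the Section 3.5 calendar, the row "In vitro/PBMC proliferation assays" shows the symbol for optional in every marked column, including Baseline.
- Calendar footnote 13 reads "In vitro (PBMC) proliferation assays will be an optional test for all patients", and the time points it names include pre-treatment on cycle 1 day 1.
- Section 5.1.2 says "These samples are optional and will be collected at the discretion of the PI". It also says the assay is not run when the absolute lymphocyte count gives too few cells. That reason is to be noted in the medical record and is not a deviation.

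Section 8 plans an exploratory analysis in two subgroups, based on "culture analyses performed on patient peripheral blood mononuclear cells prior to drug administration". Group 1 needs proliferation of at least 5,000 CPM and a 40% reduction in thymidine uptake at 10 µM ruxolitinib. Group 2 is everyone else who was treated. There is no category for patients without a result, and the plan says the expected share in group 1 is not known.

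**The concern.** Section 8 commits to an analysis that needs one measurement, taken before the first dose. Once dosing has begun, that sample cannot be obtained. One part of the protocol treats it as a test to be done; three others let it be omitted. A site that follows the optional rule will have patients who can never be placed correctly.

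What happens to them depends on how Section 8 is applied. Read literally, they join group 2, so some truly sensitive patients are counted as non-sensitive and the contrast between groups is diluted. If the analyst drops them instead, the comparison rests on patients whom the investigator chose to sample and who had enough circulating cells. Either way, only tested patients can enter group 1. This is the only subgroup question in Section 8, and it bears on the trial's rationale: Section 1.6.1 explains patient selection by ex vivo proliferation and its inhibition by ruxolitinib.

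**Working it through.** **Status of the pre-dose assay, place by place**

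| Place | Status |
|---|---|
| 2.4 lead-in with 2.4.7 | To be done; no optional label; refers to 5.1.2 |
| 3.5 calendar, Baseline column | Optional |
| 3.5 footnote 13 | Optional for all patients |
| 5.1.2 | Optional, at the PI's discretion; not run if too few cells |
| 8 | Pre-dose result defines the two subgroups |

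The first row and the next three cannot all hold as written. The plan gives no subgroup size, testing fraction or power for this analysis, so there is no figure to reproduce.

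**Effect of the literal group 2 wording**

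Assumed inputs (none is in the documents): s = share truly sensitive, 30–70%; u = share untested, independent of sensitivity; response 40% in sensitive and 10% in non-sensitive patients, a true difference of 30 points.

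- Group 1 holds only tested sensitive patients, so its response rate stays at 40%.
- Share of group 2 that is truly sensitive: q = s·u / (s·u + 1 − s).
- Group 2 response: 0.10 + 0.30·q.
- Apparent difference: 0.40 − (0.10 + 0.30·q) = 0.30·(1 − q).

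At u = 40%:

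- s = 30%: q = 0.12 / 0.82 = 0.146; difference 25.6 points.
- s = 50%: q = 0.20 / 0.70 = 0.286; difference 21.4 points.
- s = 70%: q = 0.28 / 0.58 = 0.483; difference 15.5 points.

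| Untested | Difference for s = 30 / 50 / 70% (points) | With a result, of 9 | Of 21 |
|---|---|---|---|
| 0% | 30 / 30 / 30 | 9 | 21 |
| 20% | 27.6 / 25.0 / 20.5 | 7.2 | 16.8 |
| 40% | 25.6 / 21.4 / 15.5 | 5.4 | 12.6 |
| 60% | 23.9 / 18.8 / 12.5 | 3.6 | 8.4 |

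The 9 is the planned number at the MTD or MAD, and 21 is the top of the 15–21 additional patients in Section 8. If untested patients are mostly non-sensitive the dilution is smaller; if mostly sensitive, larger.

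**Can the analysis support a test at all?**

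Exact power of a two-sided 5% Fisher test is the sum, over all outcome pairs with p ≤ 0.05, of the product of the two binomial probabilities. The larger group is taken as the sensitive one.

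- 50% v 10%, all tested: 0.38 for 11 v 10 and 0.23 for 8 v 7. An even split of these rates gives 30% overall, the target response rate in Section 8.
- 40% v 10%, all tested: 0.21 for 11 v 10 and 0.10 for 8 v 7.
- 60% v 10%: 0.59 for 11 v 10, falling to 0.22 for 5 v 5 if about half were untested and dropped. This implies about 35% overall, above the target.

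The even split is also an assumption. At response rates near the plan's own target, the comparison is descriptive even with complete testing.

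**The case against.** The governing text is not hidden. Item 2.4.7 is one line pointing to 5.1.2, which states that the samples are optional. Three places agree and the fourth defers to one of them, so labelling 2.4.7 optional would also remove the contradiction. That stands: a reader might infer that the protocol already requires the assay, but 2.4.7 takes its force only from the list's lead-in. Requiring the sample is a recommendation, not the only possible reading.

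A reader might also infer that optional testing costs the analysis most of its power. The documents do not support this. Section 8 plans no test and drops nobody; on its wording the harm is misclassification. Loss of numbers arises only if untested patients are excluded, and power is low at plausible rates anyway.

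A third inference is that, in an open-label trial, the investigator could pick patients according to outcome. The sample precedes the first dose, so selection cannot depend on observed response. Selection on baseline features is possible but not shown, since no testing fraction is given. The rule on too few cells does favour higher lymphocyte counts, and it would remain if the assay were required.

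Finally, the analysis is exploratory. That stands and sets the severity.

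**Conclusion.** The inconsistency is real and has a consequence for one analysis. The pre-dose assay is both listed as a test to be done and left to discretion, while Section 8 depends on it and has no place for patients without a result. Following the optional rule leads either to untested sensitive patients being counted as non-sensitive or, if they are dropped, to a selected and smaller comparison.

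The illustrated size is a true 30-point difference reduced to about 15.5–25.6 points with 40% untested. It rests wholly on the assumed sensitive share, testing fraction and response rates, and on testing being unrelated to sensitivity. The finding does not extend to the MTD, the response rate, safety or time to progression. Severity: minor.

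**What to change.** 1. Reconcile the passages by making the single pre-dose assay required in the calendar's Baseline column, footnote 13 and Section 5.1.2. Keep the existing exception for too few cells, with the reason recorded as 5.1.2 already provides. Leave later time points optional.
2. In Section 8, limit the comparison to patients with a pre-dose result and define group 2 as tested patients who do not meet the criteria. Show a separate not-assayed category. This is needed even after step 1, because patients with too few cells stay untested.
3. Report the numbers tested and not tested, with reasons, by ATL subtype and dose, and present the comparison descriptively.

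If the sponsor prefers to keep the assay optional, 2.4.7 should be labelled so, and Section 8 should add to steps 2 and 3 a statement that the comparison rests on a selected subset.

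The cost is a few lines of text, plus one draw of up to 50 mL and one assay in every patient with enough cells rather than only in those chosen. The draw has to fit within the blood-volume maximum referred to in Sections 5.1 and 5.1.4.
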